## E. Prosthodontic protocol

All patients will have two (possibly more) visits to receive the permanent restoration. The crown impression will be performed  $4(\pm 1)$  months after implant placement and the final restoration 3+ weeks after that. Custom abutment and screw retained implant crown will be used. Proper occlusion, crown contours, and crown margins will be confirmed in the final restoration. The subject may have to return for more than one visit for the final restoration. This is to ensure the color, contours, and margins are correct.

## F. Schedule of events

Event	Screening	CBCT visit	Implant Surgery	2 weeks PO	1 month PO	Crown impression	Crown delivery	6m	12m
Visit number	V1	V2	V3	V4	V5	V6	V7	V8	V9
Timeline			Baseline (BL)	2 (±1 day) wks	1 (± 1 wks) months	4 (±1) M after BL	3+ weeks after crown impression	6(±1)M after crown delivery	12(±1)M after crown delivery
Informed consent	SIGN		Х	Х	Х	X	Х	Х	X
Medical history	Х		Х	Х	Х	Х	Х	Х	Х
Adverse Events			Х	Х	Х	X	Χ	Х	X
Vitals (BP and HR)	Х		Х						
Dental Exam	Х								
Impressions	X Alginate					х			
CBCT Scan		Х							Х
Implant placement			х						
Clinical measurements				Х	Х	х	Х	Х	х
Periapical Radiograph *S (standardized)	X(S)		X and X(S)			х	X(S)	X(S)	X(S)
Clinical photographs	Х		Х	X			Х	х	Х
Cleaning								Х	Х
Patient compensation payment									Х

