#### **B.** Clinical assessments

Clinical measurements (probing depth, clinical attachment level and bleeding on probing) will be recorded using a UNC (University of North Carolina) manual probe. These measurements will be taken at two weeks post-operatory (V4), one month post-operatory (V5), crown impression (V6), crown restoration (V7), 6 months (V8), and 12 months (V9) after crown restoration. A tension-free caliper will be used to measure mucosa thickness at the time of surgery. Clinical photographs will be taken at each appointment as well as standardized radiographs. In addition, bone sounding procedure under local anesthesia will be performed on the mid buccal and lingual side of the implant sites at 12 month follow-up to assess the level of the underlying bone. Subjects will also be receiving a cleaning at no charge to them at their 6 and 12 month visits.

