#### C. Radiographic assessment

Intraoral radiographs will be taken using a paralleling technique with a Rinn-type film holder at the initial appointment (V1), implant placement (V3), Crown impression (V6), crown delivery (V7), and at 6 (V8) and 12 (V9) months after crown restoration. The CBCT scan will be taken at the pre-implant surgery visit (V2) and the 12 month follow up (V9). Custom-made stents will be fabricated to ensure reproducibility and standardized radiographs. All assessments will be made by one examiner. Intra-examiner calibration will be performed.

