## D. Surgical protocol

Preliminary alginate impressions will be taken at the screening appointment for the purpose of making study models to then be able to fabricate a reference stent and surgical guide. On the

implant surgery visitvital signs will be taken. Local anesthesia will be performed by using local infiltration technique with 2% Lidocaine with 1:100k epinephrine or 1:50k epinephrine. Intrasulcular and crestal incision design will be made along the crest of the ridge, bisecting the existing zone of keratinized mucosa. Full-thickness flaps are raised on the buccal and lingual/palatal side up to or slightly beyond the level of the mucogingival junction, exposing the alveolar ridge of the implant surgical sites. Once the flaps are reflected and the bone is prepared, a surgical guide will be inserted and a series of drills are used to prepare the osteotomy site incrementally. All implants will be placed according to the manufacturer's protocol (Biohorizons Tapered Internal Implant, Laser-Lok, RBT) and the rough-smooth junction will be placed to the bone crest. The buccal mucosal thickness will be measured at different levels. Implants with 9-13 mm length and 3-5 mm width will be used. After implant placement a healing abutment will be connected and interrupted sutures will be placed to close the flaps. After suturing, standardized radiographs will be obtained. Other radiographs will be taken during the surgery to check implant angulation, these will not be standardized. The surgery is being done as part of standard of care. Subjects will be instructed to rinse with warm salt water once a day every day for two weeks. All subjects will be prescribed 500mg of amoxicillin to take 3 times a day for ten days. If the subject is allergic to Amoxicillin, they will be prescribed 250 mg of Zithromax 6 tablets total /sig. 2 tablets the 1st day and Q.D. (1 x per day) until gone. In addition, the subject will be prescribed 600 mg of ibuprofen, taken as needed, for pain control. The sutures will be removed in 2 weeks.

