# IV. Outcome analysis

The measurement variables and correspondent measurement time points are summarized in the Table.

Measurement time	Measurements						
Clinical outcomes							
Baseline (V3)	Mucosa thickness						
At two weeks post-operatory (V4), one month post-operatory (V5), crown impression (V6), and at crown delivery (V7),	Probing depth, bleeding on probing, clinical attachment level						
6 (V8) and 12m (V9) after crown placement	Probing depth, bleeding on probing, clinical attachment level						
Radiographic outcome							
	Marginal bone level						
At screening (V1), implant/surgery baseline (V3), crown impression (V6), crown delivery (V7), 6m (V8), and 12m (V9) after crown placement.							

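### The schedule marks the crown-impression (V6) film as not standardized, although V6 is a marginal bone level time point and falls under the stent rule

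*Combined protocol and SAP*

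**What the plan says.** The periapical row of III.F Schedule of events, whose label begins "Periapical Radiograph *S (standardized", uses (S) to flag standardized films. V1, V7, V8 and V9 are marked X(S). V3 is marked X and X(S). V6 is marked x.

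III.D Surgical protocol explains the double mark at V3. Of the film taken at closure it says: "After suturing, standardized radiographs will be obtained". Of the films taken during the operation it says: "Other radiographs will be taken during the surgery to check implant angulation, these will not be standardized".

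III.C Radiographic assessment applies a paralleling technique and a film holder to a list of visits that, after screening, runs "implant placement (V3), Crown impression (V6), crown delivery (V7), and at 6 (V8) and 12 (V9) months after crown restoration". It then says: "Custom-made stents will be fabricated to ensure reproducibility and standardized radiographs". No visit is exempted.

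Section IV, Outcome analysis, gives the marginal bone level time points as "At screening (V1), implant/surgery baseline (V3), crown impression (V6), crown delivery (V7), 6m (V8), and 12m (V9) after crown placement".

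III.E Prosthodontic protocol places the crown impression 4 (±1) "months after implant placement and the final restoration 3+ weeks after that", so V6 comes before the crown is delivered.

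**The concern.** The documents give two instructions for one film. III.C and section IV treat V6 as a standardized bone-level reading; the schedule treats it as an ordinary film. Staff usually work from the schedule, and a film taken without the stent cannot be standardized afterwards.

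V6 is the only bone-level reading between placement and crown delivery. A difference in projection between the V3 and V6 films would enter the V3-V6 change as measurement error, and likewise any contrast from V6 to a later visit or any analysis of all visits together. Radiographic marginal bone loss is part of the primary outcome. The plan does not name the visits that define it, so use of V6 in a primary contrast cannot be excluded.

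**Working it through.** **Step 1: does a plain mark mean anything?** V3 carries both marks. III.D describes two kinds of film at that visit: angulation checks that are not standardized, and a standardized film after suturing. The two marks match the two kinds, so a mark without (S) denotes an unstandardized film.

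**Step 2: set the sections side by side, from placement onward.**

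| Visit | III.C radiograph list, stent rule | III.F schedule | Section IV bone level |
|---|---|---|---|
| V3 | listed | X and X(S) | yes |
| V6 | listed | x | yes |
| V7 | listed | X(S) | yes |
| V8 | listed | X(S) | yes |
| V9 | listed | X(S) | yes |

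V6 is the one row of five in which the schedule departs from the other two sections.

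**Step 3: which contrasts are affected?** Those with V6 as an end point (V3-V6, V6-V7, V6-V8, V6-V9) and any model that uses all visits. V3-V7, V3-V9 and V7-V9 use only films marked (S).

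**Step 4: reproduce the plan's sample size.** Inputs from section V, Sample size: difference 1.280 mm, SD 1.160 mm, two-sided alpha 5%, power 80%. The standardized difference is 1.280/1.160 = 1.103. A two-sample t test needs 13.92 per group, rounded up to 14, which is the plan's figure. Power at 14 per group is 0.802.

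**Step 5: add an assumed projection error.** The documents give no measurement error, so its SD, e, is an assumption. It is the extra error that an unstandardized film adds to a change score, independent of everything else:

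SD of the change = sqrt(1.16² + e²), with 1.16² = 1.3456.

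| e (mm, assumed) | SD of change (mm) | Power at 14 per group |
|---|---|---|
| 0 | 1.160 | 0.802 |
| 0.2 | sqrt(1.3856) = 1.177 | 0.791 |
| 0.3 | sqrt(1.4356) = 1.198 | 0.777 |
| 0.5 | sqrt(1.5956) = 1.263 | 0.733 |

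This applies the planning difference and SD to a contrast that uses V6. That is a further assumption, because the plan gives no figures for any interval ending or starting at V6.

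**The case against.** The strongest reply is that the plain x is a slip in one table cell. III.C includes V6 and allows no exception, the trial has one center, and one examiner makes all assessments. That may be so. The paralleling technique and film holder apply at V6 in any case. A reader might infer that V6 is not comparable with the other visits; the documents support only that it has not been shown to be comparable. The two instructions still conflict.

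It can also be said that (S) does not map cleanly onto use of the stent. V1 is marked X(S), yet III.D has the reference stent made from impressions taken at screening, so a V1 film taken at that visit would precede it. This is fair, but whatever (S) means, V6 is the only visit in the row without it.

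Third, V7 follows V6 by three weeks or more and is standardized, so V3-V7 already measures change up to restoration. This stands. It limits the harm to contrasts that use V6, and section V specifies none: it names only a one-way ANOVA and a t test between groups.

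Three stronger readings should be set aside:

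- **A large loss of precision.** With assumed error SDs of 0.2 mm (standardized) and 0.4 mm (not), the error variance of V3-V6 rises from 0.08 to 0.20, a factor of 2.5. That rests on one assumed pair and ignores variation between patients. Added to the planning variance, the extra 0.12 gives an SD of sqrt(1.3456 + 0.12) = 1.21 mm, about 4% above 1.16 mm.
- **Bias between groups.** Nothing in the documents suggests that projection error would differ between thin and thick mucosa. What is at issue is noise.
- **Missing films at V4 and V5.** III.B says: "Clinical photographs will be taken at each appointment as well as standardized radiographs". A reader might take this to require films at those visits too. The sentence is general, and its reference to each appointment need not govern the radiographs. III.C, the schedule and section IV agree on the radiograph visits, and none includes V4 or V5.

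**Conclusion.** The point holds as an internal contradiction that affects data collection: the schedule's mark for V6 conflicts with the stent rule in III.C and with the use of V6 in section IV. If the schedule is followed, one of the five bone-level readings from placement onward is taken without standardization in every patient.

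The effect is modest and confined to analyses that use V6: power of about 0.79 to 0.73, against 0.80 planned, for an assumed added error SD of 0.2 to 0.5 mm. The range depends on that assumption and on carrying the planning difference and SD over to such a contrast. A primary analysis of change to 12 months from V3 or V7 would be untouched. The point deserves correction because the remedy is almost free and a film taken the wrong way cannot be recovered.

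**What to change.** Choose one of two consistent positions:

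1. Mark V6 as X(S) in III.F and take that film with the stent, as III.C implies.
2. If V6 is meant to stay unstandardized, remove it from the marginal bone level time points in section IV and state the exception in III.C.

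Under either, naming in section V the visits that define marginal bone loss would settle whether V6 can enter the primary contrast.

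The first option changes one table cell. The film is already scheduled and a reference stent is already planned from the screening impressions, so it adds no visit and no scheduled exposure. The second costs two short edits and gives up the only bone-level reading between placement and crown delivery.

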# IV. Outcome analysis

The measurement variables and correspondent measurement time points are summarized in the Table.

Measurement time	Measurements						
Clinical outcomes							
Baseline (V3)	Mucosa thickness						
At two weeks post-operatory (V4), one month post-operatory (V5), crown impression (V6), and at crown delivery (V7),	Probing depth, bleeding on probing, clinical attachment level						
6 (V8) and 12m (V9) after crown placement	Probing depth, bleeding on probing, clinical attachment level						
Radiographic outcome							
	Marginal bone level						
At screening (V1), implant/surgery baseline (V3), crown impression (V6), crown delivery (V7), 6m (V8), and 12m (V9) after crown placement.							

## V. Statistical analyses

## Sample size

In this present study, test significance level ( $\alpha$ ) that is used is 5% and the power analysis is 80%. Sample size for each group is calculated using a computer program with two sided equivalence

for difference of proportions in two group design.† According to the previous study mean bone loss of implant placed in thin tissue biotype ( $\mu_1$ ) was 1.450 mm and mean bone loss of implant placed in thick tissue biotype ( $\mu_2$ ) was 0.170 mm. The difference in means in between two groups ( $\mu_1$  -  $\mu_2$ ) was 1.280 mm and common standard deviation was ( $\sigma$ ) was 1.160 mm. Therefore, the sample (n) needed in each group in this present study is 14 patients.

## **Hypothesis**

Null hypothesis is mucosa thickness does not affect implant marginal bone loss on implant with smooth collar.

## Statistical analysis

One way ANOVA will be used to detect any differences in between groups and student t test analysis will be conducted to assess mean differences between the groups.

-

†nQuery Advisor®, version 7.0., Los Angeles; Statistical Solutions Inc., 2007

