## **General Investigational Plan**

A single center, prospective controlled clinical trial is planned to investigate the effect of mucosa tissue thickness upon implant marginal bone changes on implant with smooth collar. Twenty eight adult patients who fulfill the inclusion criteria will be divided into 2 groups based upon the mucosa thickness (<2 mm and ≥2 mm). A signed written informed consent will be obtained from all subjects. Subjects will not be screened or treated until an informed consent has been obtained. Patient information will be protected according to the privacy regulations of the federal Health Insurance Portability and Accountability Act of 1996 (HIPAA).

The enrolled patients will receive implants with polished collar. Implants will be restored at 4 (±1) months after placement. Outcome analyses will be performed until 1 (±1 month) year after loading and clinical and radiographic parameters will be evaluated to compare clinical outcomes between groups. The primary outcome is implant marginal bone loss and probing depth from clinical and radiographic measurements.

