## **II.** Objectives

The primary objective of this study is to compare the amount of implant marginal bone loss radiographically and probing depth in between thin and thick mucosa group that will receive a machined collar implant.

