#### III. Treatment

#### A. Patient selection

The use of human subjects in this project will be submitted for approval by the Institutional Review Board (IRB) at the University of Michigan prior to conducting the study. Patients requiring an implant to replace a missing tooth in the premolar or 1st molar area will be recruited for this prospective controlled trial. A total of up to 40 subjects will be recruited with the goal of enrolling a minimum of 28 subjects divided into 2 groups (14 in each group) based upon the mucosa thickness (<2 mm and ≥2 mm). A prospective design will be applied and implants with a polished collar will be placed.\*

-

\* Biohorizons Tapered Internal Implant, Laser-Lok, RBT

Potential patients will be carefully screened according to the inclusion and exclusion criteria as

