#### follows:

## **Inclusion Criteria**

- Male or Female
- Aged ≥18
- In need of one dental implant in the Maxillary or Mandibular area, premolar, or 1st molar tooth
- Natural adjacent teeth
- Bone height of ≥10mm
- Bone width of ≥5mm
- Good oral hygiene
- Stable periodontium
- Willingness to fulfill all study requirements

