## **Exclusion Criteria**

- Need bone augmentation
- Need one dental implant that is anterior, a 2nd or 3rd molar tooth
- Current smoker or quit smoking less than one year
- Pregnant or plan to get pregnant
- Uncontrolled diabetes (HbA1C > 7)
- Medical conditions that may influence the outcome of the study (neurologic or psychiatric disorders, systemic infections )
- Current use of oral bisphosphonates
- History of IV bisphosphonates
- History of radiation therapy in the head and neck area within 4 years
- Poor oral hygiene (plaque score more than 40% based on O'Leary plaque score)
- Once a group has been filled, subjects who meet the criteria of that group will be excluded

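### The thickness groups are not randomised and only an unadjusted comparison is planned; a table of implant site by group and a site-adjusted sensitivity estimate would be a cheap, optional improvement

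*Combined protocol and SAP*

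**What the plan says.** **Groups.** Under General Investigational Plan, patients "will be divided into 2 groups based upon the mucosa thickness", with the cut at 2 mm. Thickness is a trait of the patient, and no randomisation is described. Section III.A (Patient selection) sets 14 per group: "A total of up to 40 subjects will be recruited with the goal of enrolling a minimum of 28 subjects". The exclusion criteria close a full group: "Once a group has been filled, subjects who meet the criteria of that group will be excluded".

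**Sites.** The inclusion criterion reads "In need of one dental implant in the Maxillary or Mandibular area, premolar" and goes on to admit first molars. Anterior, second-molar and third-molar sites are excluded. So are sites that need bone augmentation, current or recent smokers, patients with uncontrolled diabetes and patients with poor oral hygiene. Minimum bone height and width are required.

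**Outcomes.** "The primary outcome is implant marginal bone loss and probing depth from clinical and radiographic measurements". Section II (Objectives) repeats the pair: the aim is to "compare the amount of implant marginal bone loss radiographically and probing depth in between thin and thick mucosa group".

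**Analysis.** Section V, Statistical analysis, is one sentence: "One way ANOVA will be used to detect any differences in between groups and student t test analysis will be conducted", the latter to assess the mean difference. The Hypothesis paragraph of Section V states the null as thickness having no effect on marginal bone loss. The text provides no covariate, stratification, matching, site-by-group table or sensitivity analysis.

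**The concern.** In a randomised trial, chance alone would decide how arch and tooth position fall between the groups. Here the groups are formed by a trait. If thin mucosa were more common in one arch or at one tooth position, and bone loss or probing depth differed there for other reasons, the difference in means would combine the thickness contrast with the site contrast. The planned test cannot separate the two, and the planned reporting would not show the reader whether the question arises. This matters because the hypothesis concerns an effect of thickness and not merely a difference between two kinds of patient.

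**Working it through.** **1. The plan's own figure.** Inputs from Section V, Sample size: difference 1.450 − 0.170 = 1.280 mm, SD 1.160 mm, two-sided α 5%, power 80%, 14 per group.

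- SE = 1.16 × √(2/14) = 0.438 mm.
- Noncentrality = 1.28 / 0.438 = 2.92 on 26 df, so power is 80.2% (77.0% at 13 per group). The stated 14 is reproduced by a two-sided t test on means.
- 95% CI half-width = 2.056 × 0.438 = 0.90 mm.

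**2. ANOVA adds no adjustment.** With two groups the one-way ANOVA statistic equals the square of the t statistic (F = t²). The two planned tests are one unadjusted comparison.

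**3. Bias if site is related to both thickness and outcome.** The documents give no site mix and no site effect, so both are assumed. Bias = imbalance in arch × arch effect. Type I error is the simulated rejection rate of the planned t test when thickness has no effect (residual SD 1.16 mm, 14 per group, 400,000 runs per cell).

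| Imbalance | Arch effect | Bias | Share of 1.28 mm | Type I error |
|---|---|---|---|---|
| 20 points | 0.3 mm | 0.06 mm | 5% | 5.2% |
| 20 points | 0.5 mm | 0.10 mm | 8% | 5.6% |
| 20 points | 1.0 mm | 0.20 mm | 16% | 6.9% |
| 40 points | 0.3 mm | 0.12 mm | 9% | 5.8% |
| 40 points | 0.5 mm | 0.20 mm | 16% | 7.2% |
| 40 points | 1.0 mm | 0.40 mm | 31% | 13.0% |

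An arch effect of 1.0 mm is 78% of the whole planned difference (1.0 / 1.28), so the last row is extreme. No such range can be given for probing depth, because the documents state neither an SD nor an expected difference for it.

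**4. Chance imbalance.** Suppose site is unrelated to thickness and each factor splits between 30:70 and 50:50. For two independent binomials of 14, the groups differ by 3 or more patients (21 points) on one given factor with probability 0.30 to 0.34. On at least one of two independent factors the probability is 1 − (1 − p)² = 0.51 to 0.57. This does not bias the t test on average, but it is a reason to tabulate site.

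**5. Precision of an adjusted model.** Two binary covariates leave 24 df. The half-width is t × SE, with SE enlarged as site becomes associated with group. The figures assume SD 1.16 mm and covariates that explain none of the outcome.

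| Site mix | 95% CI half-width, bone loss | Power for 1.28 mm |
|---|---|---|
| Exact balance | 2.064 × 0.438 = 0.90 mm | 80% |
| Chance imbalance (average) | 0.94 mm | 77% |
| Both factors unbalanced by 40 points (average) | 1.14 mm | 61% |

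If the covariates explained 20% of the outcome variance and were balanced, power would instead rise to 87.9%.

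**6. How far the two estimates differ by noise.** With no site effect at all, the adjusted and unadjusted differences are more than 0.2 mm apart in about 11% of trials under chance imbalance. With both factors unbalanced by 40 points, the figure is about 50%.

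**The case against.** The strongest reply is that the plan already controls a good deal by restriction. Sites are limited to premolars and first molars, and smoking, diabetes, augmentation, oral hygiene and bone dimensions are all restricted. One implant system and one examiner are used. That stands: what remains is variation within the permitted range, not an absence of control.

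A reader might infer that closing a full group creates the imbalance. It does not. Sampling a fixed number per thickness group sets the group sizes and does not in itself produce confounding by site.

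A reader might also infer that the planned comparison is biased. The documents do not support that, since nothing in them ties arch or tooth position to thickness or to bone loss. Outside the most extreme scenario, type I error stays at or below 7.2%.

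Arch and tooth position are not the only factors left open; implant length and width vary too (Section III.D). Site is a reasonable choice because it is known for every patient, but the documents do not rank these factors. Nor does the plan's silence prevent a site table from being produced later. What prespecification adds is that the covariates are chosen before the results are seen.

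**Conclusion.** The point holds as an optional improvement. The groups are trait-defined, arch and tooth position vary within the eligible range, and the only planned analysis is one unadjusted comparison set against a hypothesis about an effect. Any remaining site difference would therefore enter the estimate without being examined.

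The size is conditional throughout: 0.06 to 0.40 mm of bias and a type I error of about 5 to 7%, reaching 13% only with a 40-point imbalance and a 1.0 mm arch effect. The trial remains valid as an unadjusted comparison of two groups of patients. What needs support is the step from that comparison to an effect of thickness. Adjustment for site would help with that step but would not complete it, because other patient differences could remain.

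**What to change.** In Section V, Statistical analysis, keep the t test of the two thickness groups as the planned comparison and add:

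1. A table of arch (maxilla or mandible) and tooth position (premolar or first molar) by thickness group.
2. A prespecified sensitivity analysis for each primary measure, marginal bone loss and probing depth: a linear model of the outcome on thickness group, arch and tooth position. Use the same outcome definition and time point as the t test, and report the adjusted difference with its 95% CI beside the unadjusted one.
3. A sentence that the conclusion will be stated as an association and that the adjusted estimate will be interpreted with its own interval. Agreement between the two estimates should not serve as a decision rule, because at 14 per group they often differ by noise alone.

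**Cost.** One paragraph, one table and one extra model per outcome. No visit, measurement or patient is added. The planned t test and its 80% power are unchanged. The downside is the wider adjusted interval when sites are unbalanced, which is why the model should stand as a sensitivity analysis and not replace the planned test.

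### The two named tests are one test for two groups, and with two unranked primary outcomes, several visits and no primary visit the stated 5% level is not secured

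*Combined protocol and SAP*

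**What the plan says.** Section V, Statistical analysis, is a single sentence: "One way ANOVA will be used to detect any differences in between groups and student t test analysis will be conducted" to compare the group means. Nothing else is specified: no visit, no repeated-measures method, no multiplicity rule and no handling of missing films.

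There are two groups. Section III.A aims at "enrolling a minimum of 28 subjects divided into 2 groups (14 in each group".

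The General Investigational Plan and section II both make marginal bone loss and probing depth primary, without ranking them. The General Investigational Plan adds that "clinical and radiographic parameters will be evaluated to compare clinical outcomes between groups".

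The section IV table schedules marginal bone level "At screening (V1), implant/surgery baseline (V3), crown impression (V6), crown delivery (V7), 6m (V8), and 12m (V9) after crown placement", and probing depth at V4 to V9. After surgery that is four bone-level readings and six probing readings per patient.

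The null hypothesis concerns bone loss only. The Sample size paragraph also uses bone loss only: the difference in means "was 1.280 mm and common standard deviation was" given as a value that "was 1.160 mm. Therefore, the sample (n) needed in each group in this present study is 14 patients".

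**The concern.** A plan that lists two tests suggests two separate questions, but here there is one test under two names. The sentence also does not say what that test is applied to. It could be bone loss once at 12 months, both primary outcomes at 12 months, or either outcome at every visit. These choices have different chances of a false positive, and the plan leaves the choice open until the data are in hand. The sample size, by contrast, rests on one test at 5%. If more than one comparison can count as the primary result, the trial's 5% level no longer describes it.

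**Working it through.** **Inputs from the documents.** Two groups of 14; α 5%; power 80%; difference 1.450 − 0.170 = 1.280 mm; SD 1.160 mm; bone level after baseline at V6, V7, V8 and V9; probing depth at V4 to V9.

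**Assumptions.** The documents give no within-patient or between-outcome correlations. I take 0.3–0.7 within patients (0.9 shown as an extreme), equal between all visits, and 0–0.5 between outcomes at V9.

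**1. The plan's own figure.** The standardised difference is 1.280/1.160 = 1.103.
- Normal approximation: n = 2 × (1.960 + 0.842)² × 1.160²/1.280² = 12.9, so 13 per group.
- Exact t calculation at 14 per group: non-centrality 1.103 × √(14/2) = 2.92 on 26 df, power 80.2%. At 13 per group it is 77.0%. So 14 is reproduced exactly.
- A one-sided test would need only 11 per group.

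The paragraph says "Sample size for each group is calculated using a computer program with two sided equivalence" for proportions, but it gives no proportions and no margin. Its inputs are those of a difference in means, so 14 is the size for one two-sided 5% t test on bone loss.

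**2. ANOVA against t test.** With two groups, F = t². Over 2,000 simulated data sets of 14 v 14, the largest difference between the two p-values was 6 × 10⁻¹⁶.

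**3. One test.** Bone loss at V9 only: simulated type I error 4.97%.

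**4. Both primary outcomes, V9 only.** If independent, 1 − 0.95² = 9.75%. Simulated (40,000 runs): 9.5% at cross-correlation 0 and 0.3, and 9.2% at 0.5.

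**5. A test at every visit.** Chance of at least one false positive, 14 v 14, no true difference; the independent row is 1 − 0.95^k, the others are simulated (40,000 runs):

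| Within-patient correlation | Bone loss, 4 visits | Probing depth, 6 visits | All 10 tests |
|---|---|---|---|
| independent | 18.5% | 26.5% | 40.1% |
| 0.3 | 17.3% | 24.8% | 37–38% |
| 0.5 | 15.8% | 20.8% | 33% |
| 0.7 | 13.5% | 16.6% | 28% |
| 0.9 | 9.4% | 11.1% | 19% |

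In the last column the correlation between outcomes is 0 to 0.3 times the within-patient value.

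**6. Keeping two primary outcomes.** With a Bonferroni split (0.025 each), power for the stated bone-loss effect at 14 per group is 70.4%. Reaching 80% takes 17 per group.

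**7. Which repeated-measures model.** With complete data, a random-intercept model judges the V9 contrast by the average of the visit variances. If the SD of change rises over visits, that average is too small for V9. Setting the V9 SD to 1 (illustrative values):
- SDs 0.7, 0.8, 0.9, 1.0: mean variance (0.49 + 0.64 + 0.81 + 1)/4 = 0.735. The effective critical value is 1.96 × √0.735 = 1.68, so type I error is about 9%.
- SDs 0.5, 0.6, 0.8, 1.0: mean variance 0.5625. The effective critical value is 1.96 × 0.75 = 1.47, so about 14%.

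Simulation of that model at 14 v 14 gave the same 9% and 14%. The V9 t test held 5%.

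**8. Missing V9 films.** The documents give no rate. If 2 of 14 per group lack V9, the t test on 12 per group has about 73% power. A model using V8 has an effective size of roughly 12 + 2ρ² per group, where ρ is the V8–V9 correlation. For ρ of 0.3–0.7 that is 12.2–13.0, or about 74–77% power.

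**The case against.** The best case for the plan is that it means one test. There is one null hypothesis, on bone loss. The sample size is for one mean difference in bone loss, the source effect in the Introduction is first-year bone loss, and follow-up ends one year after loading. On that reading a V9 t test holds 5% and nothing is inflated. This is the reading the documents support best, and it stands, but the analysis section never states it and two other sections name probing depth as primary as well. It can also be said that requiring both outcomes to differ would not inflate the error. That is true, but the plan does not say it.

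A reader might infer four stronger things, and the documents do not support them:
- That running both tests inflates the error. It cannot, because the p-values are identical.
- That the error rate does exceed 5%. That depends on what is tested, which the plan leaves open.
- That visits will be pooled as if they were separate patients. Nothing in the documents proposes this.
- That the earlier visits are wasted. V3 can serve as the baseline, and with complete data a mixed model with visit-specific variances gives nearly the same V9 contrast as the t test. It is also not possible to blame one analysis both for testing every visit and for ignoring the early ones.

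**Conclusion.** The concern holds as a gap in specification, not as a demonstrated error. The ANOVA is redundant but harmless. The 5% level is secured only if one outcome at one visit is fixed in advance, which the sample size presupposes and the analysis section does not do. Left open, the chance of a false positive is about 9–10% for both primary outcomes at V9 and about 13–17% for bone loss at each of V6 to V9. The first figure barely depends on the assumed correlation between outcomes. The second depends on the assumed within-patient correlation and falls to about 9% if that is 0.9. A mixed model is optional. Its gain comes mainly when V9 films are missing, and its size depends on an unknown V8–V9 correlation.

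**What to change.** In section V, Statistical analysis:
- Delete the one-way ANOVA.
- State one primary test: the between-group difference in marginal bone-level change from V3 to V9, two-sided 5%, with its 95% confidence interval.
- Make probing depth secondary and the other visits descriptive, and align the General Investigational Plan and section II.
- Use the t test for this contrast. Alternatively, to retain patients who have V6–V8 films but no V9 film, use a repeated-measures mixed model (group, visit, group by visit) with visit-specific variances (unstructured or heterogeneous covariance) and Kenward-Roger degrees of freedom. Choose between them, and name the covariance structure, in advance.
- Do not use a random-intercept model with equal variances over visits.

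This restores 5% and keeps 80% power at 14 per group. The cost is a paragraph of SAP wording and slightly more analysis if the mixed model is chosen, and probing depth no longer supports a primary claim. If the sponsor wants to keep both outcomes primary, with either one sufficient, the Bonferroni route needs 17 per group instead of 14 for the bone-loss effect.
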